## **Evaluation methods protocol**

[figure not shown]
Clinical outcome measures will be carried out at the day of restorative procedures followed by 7 days, 3 month, 6 months, and 12 months following restoration placement (attachments 7 and 8).

### **1- Pulp Vitality Tests**

- Palpation test: finger pressure will be applied to the buccal and lingual mucosal areas adjacent to the root apices attempting to locate spots tender or painful to the patient.
- Cold test: cotton pellet will be sprayed with a refrigerant (Endo-Ice, Coltène Whaledent, Cuyahoga Falls, Ohio) and placed it on the crown of the tooth for approximately 15 seconds or until the patient raises a hand to indicate that s/he felt a cold sensation and with a two minutes interval between different tests.
- Percussion: will be done using the blunt end of an instrument applying light and gentle pressure on the teeth. The teeth should be first percussed occlusally and then if no difference is discerned, the test should be repeated, percussing the buccal and lingual aspects of the teeth.

### **2- Pain assessment using VAS scale**

The **visual analogue scale (VAS)** is a psychometric response scale which is considered to be one of the best methods available for the estimation of the intensity of pain. The VAS provides a continuous scale for magnitude estimation of characteristics or attitudes that cannot be directly measured. When responding to a VAS, respondents specify their level of agreement to a statement by indicating a position along a continuous line between two end-points.

No pain

Pain as bad as it could possibly be

VAS is considered preferable to discontinuous methods, such as numerical and verbal rating scales. The main advantage of VAS has been claimed to be a high degree of 'sensitivity'. Indeed, it has a discriminating capacity superior to that of the numerical and verbal rating. In the present study, all the subjects will be asked to answer one question tracing a line on a hard copy visual analogue scale which will range from 0 to 10 (0 = no pain / 10 = pain as bad as could be). The question at the top of the visual analogue scale will be: "In a scale from 0 to 10 how would you define the pain relative to this particular tooth? Please draw a line". There will be a pain assessment at the baseline (during the initial exam), 7days, 3 months, 6 months, and 12 months (during the follow-up appointments). Each score will be kept in an excel file document and will not be shown to the subject at the time of the other pain assessments. All the data from the visual analogue scale will be classified and analyzed for statistical significance.

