**Clinical inclusion criteria:**

- Adults in good general health between 18 and 64 years of age;
- Active carious lesions deep into dentin (75% or more of dentin) involving occlusal/incisal and/or proximal surfaces of permanent teeth;
- Absence of clinical symptoms of irreversible pulpitis (spontaneous pain);
- Absence of periapical pathology, sinus tract, swelling or abnormal mobility;
- Restorable teeth.

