### **Study schedule:**

The principle investigator or study coordinator will be the initial contact. Potential subjects will be approved for screening through a brief interview and intraoral examination.

- **Screening appointment:** A screening appointment will be scheduled and potential subjects will be approved after a thorough interview and intraoral and x-ray examinations. Each subject will be provided with a written consent form to read and attest with his or her signature. Patients will be assured of the privacy of their data and will receive a 3 digit number ID. All data collected will be saved in password protected computer in the principal investigator office, room 531A (key access only). The screening process will include medical and dental history, demographics, current/concomitant medication, oral soft and hard tissue examination, and a review of all inclusion and exclusion criteria (attachment # 5 and 6). Pregnancy test will be provided to childbearing women subjects at screening appointment to rule out pregnancy (to meet inclusion/exclusion criteria). The pregnancy test to be provided is First Response Pregnancy Test Stick (Church & Dwight Co. Inc).
- Subjects who are found eligible through the screening process will be evaluated preoperatively through a periapical and bitewing radiographs (**Figure 1**). The penetration of the lesion will be assessed in the bitewing radiograph according to the inclusion criteria. To obtain period-identical x-rays, a specific film holder (Super-bite; Kerr) Rinn XCP film holder will be used. An acrylic resin (Duralay) pattern will be fabricated for each subject on the biteblock of the film holder to be able to reposition it when taking follow up radiographs. Also baseline pain assessment will be recorded via visual analogue scale (VAS); and pulp vitality assessment, using palpation, cold, percussion, and EPT tests, will be completed. Data will be collected in a form (attachments #7) and inputted into a secure, web-based Research Electronic Data Capture (REDCap) application.
- **Clinical intervention:** As for any dental appointment for caries removal, the patient's medical history will be reviewed, vital signs will be taken, and standard procedures for caries removal and restoration will be done. These include local anesthesia and rubber

dam isolation. The caries will be accessed aseptically with conventional burs and high speed hand piece instruments.

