- Resin composite (Aelite LS Posterior, Bisco) will be used incrementally (3-5 increments) to fill in the remaining cavity and each increment will be cured for 40 seconds. Patient's occlusion will be checked and adjusted if needed. Once patient is satisfied with the restoration, a bitewing radiograph will be taken as a baseline post-treatment documentation of the restoration and remaining dentin thickness (layer of dentin between the restoration and the pulp). Once the restoration is complete and the patient is satisfied, a bitewing radiograph will be taken. All subjects will be given post-operative instructions (attachment #5) and the following appointment will be scheduled. Post-operative instruction will be given to the patient.
- **Phone call follow up: 24h and 1 week:** Subject will be reached ~~interviewed~~ by phone (script) 24 hours and one week after the intervention to remind them to complete the pain assessment form. Electronic (via REDCap) or printed forms (with pre-stamped envelopes) will be provided to the subjects. Survey will ask the patient to assess their pain using the visual analog scale (attachment #8).
- **Follow up appointments at 3 months, 6 months, and 12 months after procedure:** At 3 months, only a clinical examination will be completed. At 6 and 12 months, periapical and bitewing radiographic evaluation will be performed for research purposes. Pulp vitality and

pain will be assessed at each follow up appointment using the respective forms. All gathered data will be inputted into the REDCap application. Pregnancy test will also be provided to childbearing women subjects at 6 months follow up (where x-rays will be taken for research purposes) and 12 month follow-up (where x-rays will be taken for research purposes). If pregnancy is detected during the trial, the subject will be immediately removed from the study.

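### The single VAS pain question sets no reference period, does not say whether provoked pain counts, and has no fixed place relative to the vitality tests, so scores may not be comparable between subjects or visits

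*Combined protocol and SAP*

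**What the plan says.** The instrument is fixed in the protocol under Evaluation methods protocol, 2- Pain assessment using VAS scale. There, "all the subjects will be asked to answer one question tracing a line on a hard copy visual analogue scale", running from 0 to 10, and the question is printed; after naming the scale it asks "how would you define the pain relative to this particular tooth? Please draw a line".

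The same section gives the timing: "There will be a pain assessment at the baseline (during the initial exam), 7days, 3 months, 6 months, and 12 months (during the follow-up appointments"). The Study schedule adds calls at 24 hours and one week, whose purpose is "to remind them to complete the pain assessment form". No reference period appears there either.

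On the order of assessments, the Study schedule says of the screening visit that "baseline pain assessment will be recorded via visual analogue scale (VAS); and pulp vitality assessment" will be done. For the recalls it names pulp vitality and then pain in a single sentence: "pain will be assessed at each follow up appointment using the respective forms".

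On entry, the clinical inclusion criteria require "Absence of clinical symptoms of irreversible pulpitis (spontaneous pain"). The exclusion criteria remove patients with spontaneous pain that is moderate to severe.

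**The concern.** A pain score has meaning only for a stated period and a stated kind of pain, and the printed question gives neither. Two careful subjects with the same experience could mark very different points: one has no pain in the chair and marks 0, while the other recalls a bad episode some weeks earlier and marks 6. Staff who follow the protocol to the letter would not prevent this.

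The kind of pain matters here because entry requires freedom from spontaneous symptoms of irreversible pulpitis. Brief or provoked pain may therefore be much of what the scale has to register, and the wording leaves its status open.

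The clinic visits add a second difficulty. Cold, percussion and palpation can hurt, and a VAS marked just afterwards may pick that up. Forms completed at home involve no testing.

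At stake is the only self-rated pain scale the protocol describes. Ratings collected without a defined window cannot be reinterpreted afterwards.

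**Working it through.** **Step 1. Is a reference period or a definition of provoked pain given anywhere?**

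| Place in the protocol | Reference period | Provoked pain |
|---|---|---|
| 2- Pain assessment using VAS scale (question printed) | none | not mentioned |
| Study schedule, screening visit | none | tested by palpation, cold, percussion and EPT; no VAS for these |
| Study schedule, 24-hour and 1-week calls | none | not mentioned |
| Study schedule, 3, 6 and 12 months | none | vitality tests repeated; no VAS for these |
| 1- Pulp Vitality Tests | not applicable | palpation, cold and percussion described; no pain score |
| Statistical Analysis Plan | none | not mentioned |

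Neither is supplied.

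**Step 2. How long could the implied period be?** Forms fall at baseline, 24 hours, 7 days, and 3, 6 and 12 months. A subject who answers for the time since treatment or since the last form covers about 1 day at the first form, about 6 days at the second, just under 3 months at the third, 3 months at the fourth and 6 months at the fifth. A subject who answers for the present moment covers the same period each time. Only the first reading changes with the visit.

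**Step 3. Is the order of VAS and pulp tests fixed?** The screening text names the VAS first; the recall text names vitality first, as do the numbered headings 1 and 2. All of these are lists, and none states a sequence. The order is unspecified.

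**Step 4. How large could the effect be?** The plan has no figure to reproduce: 150 teeth is stated without a significance level, power, effect size or expected rate, and no VAS mean, SD or share of zeros is given. What follows is illustration only.

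Assume the VAS is reduced to any pain against none and tested with Fisher's exact test (two-sided 5%, full enumeration), with 40 teeth per arm. Let *f* be the share of subjects who answer for the present moment. The expected rate in an arm is then

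rate = (1 − *f*) × window rate + *f* × present-moment rate.

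For assumed window rates of 50% and 20% and present-moment rates of 8% and 4%, *f* = 0.5 gives 0.5 × 50 + 0.5 × 8 = 29% against 0.5 × 20 + 0.5 × 4 = 12%, a difference of 17 points.

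| Assumed rates (window; now) | *f* = 0 | *f* = 0.25 | *f* = 0.5 | *f* = 0.75 |
|---|---|---|---|---|
| 50% v 20%; 8% v 4%: difference, points | 30 | 23.5 | 17 | 10.5 |
| power | 75% | 58% | 38% | 19% |
| 40% v 15%; 6% v 3%: difference, points | 25 | 19.5 | 14 | 8.5 |
| power | 64% | 48% | 31% | 13% |
| 30% v 20%; 8% v 4%: difference, points | 10 | 8.5 | 7 | 5.5 |
| power | 12% | 11% | 9% | 6% |

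For the first set of rates, going from *f* = 0 to *f* = 0.75 takes power from 60% to 11% at 30 per arm, and from 85% to 23% at 50 per arm.

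The dilution follows whenever the arms differ less at the present moment than over the window. Its size depends wholly on the assumed rates and on *f*.

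**Step 5. Would many zeros matter?** They would, if they occurred. A simulation with 50 teeth per arm used a Mann-Whitney test, non-zero scores from gamma distributions with means 2 and 3, and the same share of zeros in both arms. Power was about 74% with no zeros, 24% with 30% zeros and 10% with 50%. All of these inputs are assumed. The result shows that the share of zeros is important and does not show what it will be.

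**The case against.** **The question is in the present tense.** Many subjects may take it as pain now, and the more uniform that reading, the less mixing there is. This stands in part: the scores may mix two constructs, and how far they do so is unknown.

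**Provoked response is already measured.** Palpation, cold and percussion are done at baseline and at the recalls. This is true, and it would be wrong to say that the trial ignores provoked pain. These are vitality tests, however, with no pain score attached, so they do not settle what the VAS measures.

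**The arms are affected alike.** Treatment is randomised and patients are blinded. This stands: the ambiguity costs precision and interpretability, and gives no reason to expect bias towards one material.

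**The power figures rest on assumptions.** They do, and they also reduce a 0 to 10 scale to pain or no pain. The third set of rates shows a case where the trial would say little about pain however the question was worded.

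**The form itself may say more.** Attachment 8 is not among the pages supplied, so a further instruction on it cannot be excluded. Against that, the protocol says what stands at the top of the scale and that there is a single question.

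Two stronger readings are tempting. A reader might infer that scores will mostly be zero because spontaneous pain bars entry. The entry criteria apply before treatment, leave room for mild or provoked pain, and say nothing about pain a day or a week after deep excavation. A reader might also infer that the recall visits put the vitality tests before the VAS; the text lists the two and sets no sequence.

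**Conclusion.** The defect in the instrument is established. The one VAS question has no reference period, does not say whether provoked pain counts, and is not placed before or after the pulp tests. Scores may therefore not be comparable between subjects, or between visits in the same subject, even when the protocol is followed exactly.

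The consequence is noise and blurred interpretation, with no direction favouring an arm. Its size cannot be derived from the documents. The illustrations run from a large loss of power (75% to 38% when half the subjects answer for the present moment) to a negligible one (12% to 9%), according to the assumed rates. A floor effect is plausible but not shown.

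The VAS is not named as the primary outcome and is not among the criteria for radiographic success. This is a cheap improvement to make, and it does not call the trial's main comparison into question.

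**What to change.** Three changes to the pain assessment section, carried through to attachment 8:

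1. Add one explicit reference period to the question, the same on every form; for example, the worst pain from this tooth in the past 24 hours. A 24-hour window on one form and 7 days on the others would recreate the problem.
2. Say in the question whether pain on biting or with cold is to be included. If both kinds are of interest, two separate items are clearer than one merged score.
3. State that the VAS is completed before palpation, cold, percussion and EPT at baseline and at every recall.

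The cost is one phrase on the form and one line on the order of assessments. No visit, test or subject is added, unless the second item is chosen. There is a small downside: the answer depends on short-term recall, and a short window misses pain earlier in the interval, which matters most at 3, 6 and 12 months.

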### **3- Radiographic outcome measures:**

The criteria used to determine a successful radiographic outcome of the indirect pulp capping treatment is: (1) absence of interradicular or periapical radiolucencies, (2) absence of increased PDL space, (3) absence of resorptive defects all determined by periapical and bitewing radiographs. Radiographic assessment will be made through bitewings and periapical radiographs the day of intervention followed by the 6 and 12 months recalls as part of regular assessment and to collect research data. Teeth that present with clinical or radiographic signs or symptoms of irreversible pulpitis or necrosis will be assessed by an endodontist for proper endodontic treatment. Patient may be subjected to additional x-rays following pulp capping therapy for proper diagnosis of complications from treatment.

Radiographic research data collection: As part of research data collection, attempt will be made to assess changes to the remaining dentin thickness between recall appointments. To obtain period-identical x-rays, a specific film holder (Super-bite; Kerr) Rinn XCP film holder will be used to take bitewings. Software program (Dexis) will be used to measure digitally the remaining dentin thickness in 5-8 areas. The values will be averaged for estimated thickness.

### **Data handling and Interpretation**

Data entry and database management will be done in an ongoing manner by project staff. All data will be entered in a timely manner once collected. The database will be password protected and housed in a secure location. The database will be backed up on a regular schedule with backup copies stored in a separate location from the primary file server. Quality of data entry will be enhanced by double entry data forms with field and range validation. Project management tools include graphical interfaces for tracking timeliness of data entry, missing data, graphical reports of actual recruitment versus recruitment goals on a real-time basis (i.e., updated as each participant is entered into the system), and other reports. The goal is 100% data accuracy.

Data and/or information which identifies the subject and the signed consent form may be looked at and/or copied for evaluation of the research protocol by: UIC Office for the Protection of Research Subjects, State of Illinois Auditors, State of Illinois Auditors and the research sponsor (Bisco Dental Products).

**Statistical Analysis Plan:** Descriptive data and rates of success will be calculated independently for indirect and direct therapies. Statistical analyses of proportions will be done using Fisher's test and 95% confidence intervals (CI).

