## **Study Protocol**

**Study design:** Prospective, randomized, controlled, double-blinded study with three treatment arms.

**Sample size:** 150 teeth with deep caries of subjects willing and able to return to UIC COD for recall purposes.

**Eligibility criteria:** Subject must meet the inclusion criteria to participate in the study.

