## **Subject management and recruitment process**

Recruitment flyers (attachment #1) will be posted in different locations at the University of Illinois at Chicago campus.

Recruitment e-mails and messages will be sent to all the faculty and students attending predoctoral and postdoctoral clinics at UIC College of Dentistry. We will also send recruitment messages to all faculty, staff and students at the University of Illinois at Chicago using campus wide massmail listservs. In addition, medical records will be reviewed to determine subject eligibility.

Those subjects who will volunteer to participate will be asked to contact via phone the principle investigator or study coordinator, to comply with the inform consent process (attachment #3 – phone call script).

Once patients have been properly screened and approved for the study, the selection of the treatment that they will receive will be carried out randomly, using random integer generator ([www.random.org/integers/](http://www.random.org/integers/)). Teeth of subjects will be first stratified into those needing indirect pulp capping and direct pulp capping. Based on stratification, subjects will be randomized to one of three arms (indirect pulp capping) or one of two arms (direct pulp capping). Patients will be blinded to the treatment.

Subjects will be compensated in cash for their participation in the study.

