### **Clinical Protocol: Operators' calibration**

The study will be carried out in the UIC College of Dentistry, Clinical Research Center. The investigators will be calibrated for case selection using bitewing and periapical radiographs representing different lesion depths. Initial radiographs will be evaluated independently for root maturity, bridge formation, and periradicular status by two examiners blinded to the technique, with forced consensus in cases of disagreement.

All restorative procedures will be performed by three calibrated clinicians, who will use the 3 different lining/sealers materials in equally distributed subjects.

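### For two-arm comparisons Fisher's test is valid but conservative; a fully specified Boschloo exact test would keep the 5% limit and usually add some power at almost no cost

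*Combined protocol and SAP*

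**What the plan says.** The Statistical Analysis Plan paragraph under Data handling and Interpretation is two sentences long. The first separates the strata: "Descriptive data and rates of success will be calculated independently for indirect and direct therapies". The second names the method: "Statistical analyses of proportions will be done using Fisher's test and 95% confidence intervals (CI". It does not give a significance level or sidedness, or say whether the three indirect arms are compared pairwise or by one global test.

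The sample size under Study Protocol is a single total: "150 teeth with deep caries of subjects willing and able to return to UIC COD for recall purposes". Under Subject management and recruitment process, "subjects will be randomized to one of three arms (indirect pulp capping) or one of two arms (direct pulp capping". The split between strata, the numbers per arm, the expected success rates and the target power are not stated. On balance, the same section says that "the selection of the treatment that they will receive will be carried out randomly, using random integer generator", and describes no blocking. The operators' calibration section expresses an aim of balance, with three clinicians "who will use the 3 different lining/sealers materials in equally distributed subjects".

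**The concern.** The total of 150 teeth is divided over five stratum-by-arm cells, and the strata are analysed separately, so each two-arm test uses only part of the total. Fisher's test conditions on both margins of the table. With few failures, very few tables are possible once the margins are fixed, and the achievable p-values jump in coarse steps. The real false-positive rate then falls well short of the nominal level, and power falls with it.

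Boschloo's test starts from the same Fisher p-value but calibrates its cut-off over the unknown common success rate. It can therefore use some of the error allowance that Fisher leaves unspent. In a small trial that is a gain without recruiting more teeth.

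**Working it through.** **The plan's own figure.** There is none to reproduce: no power, effect size or alpha is stated.

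**Inputs.**
- From the documents: 150 teeth, three indirect arms, two direct arms, separate analyses, proportions of success.
- Assumed: two-sided 5% (suggested only by the 95% intervals); common success of 80 to 95% under the null; under the alternative, 85 to 95% in one arm and 15 to 30 points less in the other; teeth independent.
- Assumed arm sizes: five equal cells give 150/5 = 30. A 100/50 split gives 100/3 ≈ 33 and 50/2 = 25. A 75/75 split gives 75/3 = 25 and 75/2 ≈ 37 or 38.

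**Method.** Let F(a,b) be the two-sided Fisher p-value for a successes of n1 and b of n2. A test rejects on the set R = {(a,b): F(a,b) ≤ c}.
- Fisher uses c = 0.05.
- Boschloo uses the largest c for which the maximum over p of Σ_R Bin(a; n1, p)·Bin(b; n2, p) is at most 0.05. The maximum was taken over a 999-point grid of p.
- Power is the same sum with p1 and p2 in place of p.

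Fisher is itself valid, so Boschloo's c is never below 0.05. Its rejection set therefore contains Fisher's.

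**One table by hand.** Take 33 per arm, with 32/33 against 26/33 (8 failures in all).
- P(0 failures in the first arm) = C(33,8)/C(66,8) = 0.0024.
- P(1 failure) = 33·C(33,7)/C(66,8) = 0.0245.
- Two-sided Fisher p = 2 × (0.0024 + 0.0245) ≈ 0.054, so Fisher does not reject.
- At 33/33 Boschloo's c is 0.077, with maximum size 4.85%. Boschloo rejects.

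**Actual size of Fisher (%) at a common success rate of:**

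| Arms | 80% | 85% | 90% | 95% |
|---|---|---|---|---|
| 25/25 | 2.22 | 1.89 | 0.88 | 0.08 |
| 30/30 | 2.22 | 1.72 | 0.94 | 0.15 |
| 33/33 | 2.38 | 1.99 | 1.15 | 0.21 |
| 25/30 | 2.96 | 2.71 | 2.23 | 0.87 |
| 28/32 | 3.66 | 3.30 | 2.62 | 1.14 |
| 38/37 | 3.70 | 3.45 | 2.45 | 0.76 |

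Boschloo at 33/33 gives 4.02, 3.30, 2.59 and 0.92. Its maximum size was below 5% in every pair checked.

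**Power, Fisher to Boschloo.**
- 33/33: 95 v 75%, 50.6 to 58.9%; 90 v 70%, 42.1 to 50.5%; 90 v 65%, 59.7 to 68.2%. Fisher needs about 37 to 38 teeth per arm to match Boschloo at 33.
- 25/25: 95 v 75%, 37.0 to 44.9%.
- 30/30: 90 v 65%, 54.5 to 59.4%.

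**Gain over the whole grid of alternatives.**
- Equal arms of 25 to 33: 3.4 to 13.9 points, with means by arm size from 5.5 to 10.8.
- 50/50: 1.0 to 7.5 points, mean 4.1.
- Unequal arms (differences of 1 to 8 teeth): 0 to 12.5 points, with means by pair from about 2 to 6. The extremes depend on which arm is smaller. At 25/30 the gain ranges from 0.0 to 12.5.

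**Three arms at once.** A global 3×2 Fisher test at 25 to 33 per arm has size 4.1 to 4.4% at 80% success, 3.0 to 3.9% at 90% and 1.4 to 2.1% at 95%.

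**Variant.** Some software defines the two-sided Boschloo p as twice the smaller one-sided p. For 25/33 against 32/34, Fisher gives 0.0446 and that doubled version gives 0.0502. At 38/37 the doubled version loses up to 4.2 points of power against Fisher.

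**The case against.** The strongest reply is that nothing is wrong. Fisher's test is valid and familiar, and the plan promises no power that it then fails to deliver. At 33 per arm and 95 v 75%, power is 51 or 59%, low either way. The missing sample-size rationale and the unspecified comparisons matter more. All of this stands, and it is why the point is an optional improvement.

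Three stronger readings that a reader might infer do not hold.
- **A fixed gain of 5 to 10 points.** This is a central figure for exactly equal arms, under sizes and rates the documents do not give. The random integer generator is described without blocking, and teeth may be lost before 12 months, so exact balance at analysis is unlikely. Unequal arms raise Fisher's size and shrink the gain, sometimes to nothing.
- **Fisher far below 5% throughout the trial.** The plan does not say that the indirect arms are compared pairwise. A global three-arm test would be much nearer its nominal level, at least at 80 to 90% success.
- **Any Boschloo test rejects whenever Fisher does.** That is true only when the two-sided Fisher p-value orders the tables. The doubled version breaks it.

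**Conclusion.** A low-cost efficiency gain, confined to two-arm comparisons. Under the assumed 25 to 38 teeth per arm, 80 to 95% success and a two-sided 5% level, Fisher's actual size is about 0.1 to 3.7%. Boschloo's test in the specified variant keeps the 5% limit and never rejects fewer tables. The benefit is typically 5 to 10 points of power with equal arms and 0 to about 12, often 2 to 5, with unequal arms. These figures would move with the true stratum split, the success rates and losses to follow-up. The documents do not support calling Fisher's test a mistake, or the trial invalid because of it.

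**What to change.** In the Statistical Analysis Plan paragraph, for two-arm comparisons, replace Fisher's test with wording such as: 'Boschloo's unconditional exact test, two-sided 5%, ordering tables by the two-sided Fisher p-value (not the doubled one-sided p-value), with a score-based 95% confidence interval for the difference in success rates.' Fisher's p-value may be shown alongside. Say in the same place whether the indirect stratum is tested globally or pairwise, because the change applies only to pairwise tests. Fix the wording before outcomes are compared, since a later switch would look selective.

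The cost is one sentence and a check of the implementation, because default software may use the doubled variant. The test is less familiar to readers. The score interval is not its exact inverse, so the two can disagree near the boundary, and the plan should state that the test governs.
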